13 STUDY ADMINISTRATION

13.A Review and Consent Requirements

13.A.1 Institutional Review Board (IRB)

The investigator will supply all necessary documents to be submitted to the IRB and will ensure that the institution has a properly structured research committee. The University of Arizona Human Subjects Protection Program will be the IRB of record. Documentation of initial and ongoing reviews, submission of serious adverse event reports, study amendments and revisions, and consent form modifications will be required. This documentation is to be forwarded to:

• Consent Forms:

[name]

Clinical Research Coordinator

The University of Arizona Cancer Center – North Campus

Room 2111

[name]

[name]

• Regulatory Documents:

[name]

Lymphoma Program Regulatory Coordinator

The University of Arizona Cancer Center, Room 1955

[name]

[name]

13.A.2 Patient Information and Informed Consent

Written informed consent will be obtained for this study from all patients. The investigator or his/her staff will explain the nature of the study and the risks involved to each patient prior to his/her inclusion in the trial. The patient will also be informed that he/she is free to withdraw from the study at any time. Original, signed informed consent forms for patients registered from the University of Arizona Cancer Center will be kept at The University of Arizona Cancer Center, North Campus, room 2111.

13.B Registration Procedure

All ethical, regulatory, technical, and scientific approvals must be in place before study registrations will accepted. All patients will be registered centrally with the Clinical Research Coordinator based at [contact] prior to the initiation of treatment. The Clinical Research Coordinator will assign each patient a sequential number prior to registration. The fully signed informed consent must be presented and all inclusion and exclusion criteria will be reviewed with the registering investigator or designee. All source documentation needed to confirm eligibility must be available for this review. A second phone registration is required prior to the initiation of Zevalin® to confirm eligibility and dose of therapy.

13.C Study Records - Data Collection & Recording

Study-specific data forms are to be found in the Clinical Research Services clinical database. All forms are to be submitted centrally to the Clinical Research Coordinator at the University of Arizona Cancer Center at baseline, completion of ESHAP cycle 1, completion of ESHAP cycle 2, restaging at Cycle 2, Day 29, completion of Zevalin®, and at the follow-up intervals specified in Appendix A, including at time of relapse/progression, second malignancy, or death.

13.D Patient Confidentiality

The information obtained as a result of this research is confidential and all efforts must be made to ensure that the patient's anonymity will be maintained. All records, evaluation forms, and reports will be identified by an identification code to maintain confidentiality. A log of patients' codes, names and addresses will be kept separately. All records are to be kept in locked files.

13.E Monitoring

This research study is an investigator-sponsored trial. The Arizona Cancer Center has an NCI-approved Data and Safety Monitoring Plan for clinical research. Data and systems for participating in the study will be monitored according to procedures outlined in that plan, with centralized patient screening and registration, submission and review of data, and initial verification of data as summarized below.

Protocol Data and Safety Monitoring Plan (Medium Risk)

Medium risk studies are intended to include all trials involving therapeutic intervention(s), which are **not** designated as high risk per NCI and the IND is not held by the investigator.

Data and Safety Monitoring Plan:

1. Identification of the DSMB obligated for oversight responsibilities:

The Arizona Cancer Center Data and Safety Monitoring Board (DSMB) will provide ongoing oversight for this trial.

2. Identification of the entity obligated for routine monitoring duties:

Routine monitoring will be provided by the Quality Assurance/Quality Control (QA/QC) Program to ensure that the investigation is conducted according to protocol design and regulatory requirements.

3. Monitoring progress and data review process:

Routine monitoring of subject data will be conducted at least every six months.

The first routine monitoring visit will include at a minimum:

• Informed consent – 100% of cases enrolled;

- Subject eligibility 50% of cases, up to two subjects;
- Data review 50% of cases, up to two subjects.

All subsequent monitoring visits will consist of randomly selected subject cases based on current enrollment and include continuing review of previously selected cases, as applicable.

A monitoring visit report and follow-up letter will be completed within two weeks of the routine monitoring visit; a copy will be maintained in the study file. A query/finding form will also be completed by the monitor to request additional source documentation, clarification, information or corrections to the CRF and/or regulatory records. The Clinical Research Coordinator or other applicable staff responsible for the study will be given a copy of this form for resolution of queries/findings. The query/finding form will be maintained with a copy of the visit report for follow-up at the next monitoring visit.

The Principal Investigator will ensure the accuracy, completeness, legibility and timeliness of the data reported in the Case Report Form (CRF). Source documentation supporting the CRF data should indicate the subject's participation in the trial and should document the dates and details of study procedures, adverse events, and patient status.

Case report forms, which include the inclusion/exclusion criteria form, adverse event forms and serious adverse event forms [other forms, depending on study] should be completed with a black ball-point pen or typed. Corrections to the forms should not obscure the original entry and should be made by striking the incorrect information with a single line. Each strike should be accompanied by the initials of the corrector and the correction date. All subject forms and study files will be stored in a secure area limited to authorized staff.

Note: Routine monitoring of regulatory documents and test article will be conducted at least annually.

4. Process to implement study closure when significant risks or benefits are identified:

This study may be prematurely terminated, if in the opinion of the investigator there is sufficient reasonable cause.

Circumstances that may warrant termination include, but are not limited to:

- Determination of unexpected, significant, or unacceptable risk to patients
- Failure to enter patients at an acceptable rate
- Insufficient complete and/or evaluable data

5. Description of adverse events and reporting procedures:

ADVERSE EVENTS

An adverse event (AE) is any untoward medical occurrence in a patient or clinical investigation subject administered a pharmaceutical product and that does not necessarily have a casual relationship with this treatment. An AE can therefore be any unfavorable and unintended sign, symptom, or disease temporally associated with the use of a medicinal (investigational) product, whether or not related to the medicinal (investigational) product.

Any and all adverse events will be recorded on the UMC adverse events record form and reviewed by the Principal Investigator.

All adverse events will be classified using either the MedDRA term or NCI Common Terminology Criteria for Adverse Events (CTCAE) version 3.0 and will address:

- Grade
- Relationship to study drug(not related, unlikely, possible, probable, definitely)
- Causality other than study drug (disease related, concomitant medication related, intercurrent illness, other)
- Date of onset, date of resolution
- Frequency of event (single, intermittent, continuous)
- Event outcome (resolved, ongoing, death)
- Action taken (none, held, dose reduced, discontinued, medication given)

SERIOUS ADVERSE EVENTS

A serious adverse event (SAE) is any untoward medical occurrence that at any dose:

- 1) Results in death;
- 2) Is life-threatening;
- 3) Requires in-patient hospitalization or prolongation of an existing hospital stay;
- 4) Results in disability persistent or significant disability/incapacity, or:
- 5) Is a congenital anomaly/birth defect.

Note: A SAE may also be an important medical event, in the view of the investigator that requires medical or surgical intervention to prevent one of the outcomes listed above.

All serious adverse events, regardless of attribution, and any deaths will be reported within 24 hours of notification of the event to the sponsor and DSMB Coordinator. All serious adverse events, regardless of attribution, and any deaths will be reported within 5 days of notification of the event to the University of Arizona Human Subjects Protection Program.

All serious adverse events will be processed by the DSMB Coordinator monthly for initial trend analysis and fully reviewed by the DSMB, every six months. The DSMB coordinator will review the SAE reporting process to confirm reporting requirements are met.

6. Plan for assuring data accuracy and protocol compliance:

Routine study activity and safety information will be reported to the DSMB every six months, or more frequently if requested. These reports will include:

- Study activity, cumulative and for the period under review;
- Safety (narrative description on non-serious and serious adverse events);
- Predetermined protocol early stopping rules for efficacy/futility;
- Monitoring and protocol compliance;
- Comments;
- Attachments (AE data reviewed by the PI to compile the report, SAE letters and reports, results of any review(s), applicable correspondence with the IRB or other regulatory agencies.

Data, safety and study progress will be reported to:

- Human Subjects Protection Program (IRB) at least annually;
- Sponsor (if applicable) at least every six months.

7. Identification of the sponsor or funding agency, as applicable:

The PI will immediately notify; in writing, the funding agency, if applicable, any action resulting in a temporary or permanent suspension of the study.

APPENDIX A

STUDY CALENDAR

4/1/2010

STUDY CALENDAR Page 1

					Ibritumomab Tiuxetan (Zevalin)			
Required Studies	Baseline	ESH	AP Treatm	ent		Regin	nen [∞]	
Visits (weeks or days)	Within28 days prior to C1, D1	Cycle 1 Day 1	Cycle 2 Day1	Cycle 2 Day 29	Day 1	Day 2,3,4,5	Day 7, 8, or 9	Day 35
PHYSICAL								
History / Physical / vital signs ^α	X		X	X	ΧП			
Height / Weight / BSA / PS	X		X	X	ΧП			
Disease Assessment	X			X				
Toxicity Assessment	X		X	X	ΧП			
LABORATORY								
CBC / differential / platelets	X		X	X	ΧП			\mathbf{X}^{Σ}
Serum Creatinine / BUN	X		X	X	ΧП			
AST/ ALT/ Alk. Phos/ T. Bilirubin^	X							
LDH	X							
BHCG [†]	X							
Beta 2- microglobulin	X							
Hepatitis B screen*	X							
Pathology Review [£]	X							
Bone marrow cytogenetics [¥]	X			X				
Bone marrow aspiration and Bx	X			X				
SCANS								
CT or PET Chest	X			X				
CT or PET Abdomen	X			X				
CT or PET Pelvis	X			X				
Gamma Scan						X≠		
TREATMENT								
ESHAP		X	X					
Rituximab 250 mg/m2					X		X	
Ibritumomab Tiuxetan Indium (¹¹¹ In Zevalin)					X			
Ibritumomab Tiuxetan Ytrium-90 (90Y Zevalin)							X	

- α Vital Signs consist of BP, temperature and pulse
- t Baseline for women of childbearing potential
- ¥ A scan is performed at 48-72 hours after 111In Zevalin. Another optional scan may be performed at 90-120 hours after 111In Zevalin.
- ∞ ¹¹¹In Zevalin is administered 4-6 weeks after completion of ESHAP.
- ٨ Required at Baseline and Encouraged to repeat as clinically indicated by Good Medical Practice.
- Encouraged by Good Medical Practice, but not required.
- ¥ Bone Marrow cytogenetics can be done at either Baseline or C2,D29, but must be done at least once.
- £ Pathology Review consists of a basic review of a pathology report. If possible submit: Representative H&E stained slides from the diagnostic biopsy, one representative paraffin block and one copy of the pathology report.
- Σ Starting Day 35 (+/- 7 days) a CBC w/ Diff and Platelet count should be done every week until nadir.
- Within 28 days prior to Rituximab & Zevalin administration..

STUDY CALENDAR Page 2

Required Studies	Restaging	Short-Term Follow-Up				Long-Term Follow-Up	Off-Study [#]
Visits (weeks or days)	3 mos post ⁹⁰ Y Zevalin	6 mos post Zevalin	12 mos post Zevalin	18 mos post Zevalin	24 mos post Zevalin	Follow-Up: Annually for 3 years [£]	Disease Progression or Removed from Study (within 4 weeks)
PHYSICAL							
History / physical / vital signs ^α	X	X	X	X	X	X	X
Height/Weight /BSA/PS	X	X	X	X	X	X	X
Disease Assessment	X	X		X		X	X
Toxicity Assessment	X	X	X	X	X	X	X
LABORATORY							
CBC/differential/platelets	X	X	X	X	X	X	X
Serum Creatinine/BUN	X	X	X	X	X	X	X
LDH	X	X	X	X	X	X	X
X-RAYS AND SCANS							
CT or PET chest	X	X		X		X	X
CT or PET Abdomen	X	X		X		X	X
CT or PET pelvis	X	X		X		X	X

- Ω After completion of post Zevalin restaging, follow-up exams and tests are to be repeated every 6 months for 2 years, and then annually for up to 3 years.
- # Off-Study Tests to be Performed When a Patient is Determined to Have Disease Progression or is Removed from the Study for any Reason. These tests will be performed within 4 weeks after a patient has demonstrated progression of disease, or removed from study. These tests do not have to be repeated if they were performed within 7 days prior to documentation of disease progression.
- α Vital signs consist of BP, temperature and pulse
- Follow-up should occur every 6 months (+/- 30 days) for 2 years after the completion of the Short-Term Follow-Up period.
- £ Continued Follow-Up should occur annually (+/- 30 days) for survival and disease status. Patients should be followed by physical exam and, if clinically indicated by Good Medical Practice, CT scans. Patients will be followed for 3 years or until patient starts an alternate treatment or is removed from study to allow determination of study endpoints.

APPENDIX B

PERFORMANCE STATUS SCALE

STATUS ^{1,2} (Karnofsky)	SCA	LE	"WHO" - STATUS ^{3,4} (Zubrod-ECOG)
Normal, no complaints	100	0	Normal activity
Able to carry on normal activity Minor signs or symptoms of disease	90	1	Symptoms, but ambulatory
Normal activities for effort	80		
Cares for self, unable to carry on normal activity or to do active work	70	2	Some bed time, but in bed less than 50% of normal daytime
Requires occasional assistance, but able to care for most of own needs	60		
Requires considerable assistance and frequent medical care	50	3	Needs to be in bed more than 50% of normal daytime
Disabled, requires special care and Assistance	40		
Severely disabled, hospitalization indicated though death not Imminent	30	4	Unable to get out of bed
Very sick, hospitalization necessary, active supportive treatment Necessary	20		
Moribund	10		
Dead	0		

- 3. Zubrod, C.G., et.al. Appraisal of Methods for the Study of Chemotherapy of Cancer in Man. Journal of Chronic Diseases. 11: 7-33, 1960
- 4. WHO Handbook for Reporting Results of Cancer Treatment. WHO Offset Publication No.48. World Health Organization, Geneva, 1979

APPENDIX C

ADULT TOXICITY CRITERIA (CTC)

Common Terminology Criteria for Adverse Events v3.0 (CTCAE)

Publish Date: August 9, 2006

Quick Reference

The NCI Common Terminology Criteria for Adverse Events v3.0 is a descriptive terminology which can be utilized for Adverse Event (AE) reporting. A grading (severity) scale is provided for each AE term.

Components and Organization

CATEGORY

A CATEGORY is a broad classification of AEs based on anatomy and/or pathophysiology. Within each CATEGORY, AEs are listed accompanied by their descriptions of severity (Grade).

Adverse Event Terms

An AE is any unfavorable and unintended sign (including an abnormal laboratory finding), symptom, or disease temporally associated with the use of a medical treatment or procedure that may or may *not* be considered related to the medical treatment or procedure. An AE is a term that is a unique representation of a specific event used for medical documentation and scientific analyses. Each AE term is mapped to a MedDRA term and code. AEs are listed alphabetically within CATEGORIES.

Short AE Name

The 'SHORT NAME' column is new and it is used to simplify documentation of AE names on Case Report Forms.

Supra-ordinate Terms

A supra-ordinate term is located within a CATEGORY and is a grouping term based on disease process, signs, symptoms, or diagnosis. A supra-ordinate term is followed by the word 'Select' and is accompanied by specific AEs that are all related to the supra-ordinate term. Supra-ordinate terms provide clustering and consistent representation of Grade for related AEs. Supra-ordinate terms are not AEs, are not mapped to a MedDRA term and code, cannot be graded and cannot be used for reporting.

REMARK

A 'REMARK' is a clarification of an AE.

ALSO CONSIDER

An 'ALSO CONSIDER' indicates additional AEs that are to be graded if they are clinically significant.

NAVIGATION NOTE

A 'NAVIGATION NOTE' indicates the location of an AE term within the CTCAE document. It lists signs/symptoms alphabetically and the CTCAE term will appear in the same CATEGORY unless the 'NAVIGATION NOTE' states differently.

Grades

Grade refers to the severity of the AE. The CTCAE v3.0 displays Grades 1 through 5 with unique clinical descriptions of severity for each AE based on this general guideline:

Grade 1 Mild AE

Grade 2 Moderate AE

Grade 3 Severe AE

Grade 4 Life-threatening or disabling AE

Grade 5 Death related to AE

A Semi-colon indicates 'or' within the description of the grade.

An 'Em dash' (—) indicates a grade not available.

Not all Grades are appropriate for all AEs. Therefore, some AEs are listed with fewer than five options for Grade selection.

Grade 5

Grade 5 (Death) is not appropriate for some AEs and therefore is not an option.

The DEATH CATEGORY is new. Only one Supra-ordinate term is listed in this CATEGORY: 'Death not associated with CTCAE term – *Select*' with 4 AE options: Death NOS; Disease progression NOS; Multi-organ failure; Sudden death.

- · Grade 5 is the only appropriate Grade
- This AE is to be used in the situation where a death
- 1. cannot be reported using a CTCAE v3.0 term associated with Grade 5, or
- 2. cannot be reported within a CTCAE CATEGORY as 'Other (Specify)'

Please refer to http://ctep.cancer.gov/reporting/ctc.html for specific Advese Event grading and reporting.

APPENDIX D

INTERNATIONAL WORKSHOP STANDARDIZED RESPONSE CRITERIA FOR NON-HODGKIN'S LYMPHOMAS

1. RESPONSE CLASSIFICATIONS

The definition of "complete disappearance" of clinically detectable disease varies. Patients considered disease-free have been defined by variables including complete blood count (CBC), clinical and radiologic findings, and sizes of lymph nodes, spleen, and liver. Additionally, the lack of bone marrow involvement may be required. Some investigators have set a minimal duration for the absence or reduction of disease before the response is confirmed^[1-11]. In some, responses are reclassified retrospectively.

Because of the considerable variation in the literature, specific, standardized guidelines for response assessment were recently established in a 1998 report from an International Workshop conducted at the NCI. Recommendations were presented to ensure accurate and objective evaluation of the presence or lack of disease, and comparability among clinical trials. The recommended criteria were based on lymph node biopsy and bone marrow evaluation and considered as anatomic definitions. Categories were included for CR, CR/unconfirmed (CRu), PR, and relapse/progression [12]. Flow cytometric, cytogenetic, and molecular studies were not included in response definitions (Table 1).

Table 1
International Workshop Response Criteria for Non-Hodgkin's Lymphoma

Response Category	Physical Examination	Lymph Nodes	Lymph Node Masses	Bone Marrow
CR	Normal	Normal	Normal	Normal
CRu	Normal	Normal	Normal	Indeterminate
	Normal	Normal	> 75% decrease	Normal or indeterminate
PR	Normal	Normal	Normal	Positive
	Normal	≥ 50% decrease	≥ 50% decrease	Irrelevant
	Decrease in liver/spleen	≥ 50% decrease	≥ 50% decrease	Irrelevant
Relapse/ progression	Enlarging liver/spleen; new sites	New or increased	New or increased	Reappearance

Adapted from Cheson et al., 1999^[12]

In addition, definitions were recommended for end points of interest in clinical trials, including survival (overall, event-free, progression-free, and disease-free), as well as response duration, time to next treatment, and cause-specific death (Table 2).

Amendment #9: 08/28/2017

Table 2
International Workshop Definitions of End Points for Clinical Trials

End Point	Response Category	Definition	Point of Measurement
Overall survival	All patients	Death from any cause	Entry onto trial
Event-free survival	CR, CRu, PR	Failure or death from any cause	Entry onto trial
Progression-free survival	All patients	Disease progression or death from NHL	Entry onto trial
Disease-free survival	CR, CRu	Time to relapse	First documentation of response
Response duration	CR, CRu, PR	Time to relapse or progression	First documentation of response
Time to next treatment	All patients	Time when new treatment is needed	Entry onto trial
Cause-specific death	All patients	Death related to NHL	Death

Adapted from Cheson et al., 1999^[12]

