Second, although ESHAP is very active in low-grade NHL, it is not often utilized by community oncologists as a salvage regimen. Therefore, most pretreated patients have not seen these agents and therefore their lymphomas should be responsive to ESHAP. After treatment with two cycles of preparative ESHAP most patients should have minimal residual disease and therefore have higher response to Zevalin. It is our hypothesis that tumor mass reduction with standard chemotherapy in relapsed follicular lymphoma will result in a significant prolongation of time to progression following Zevalin therapy, changing the natural history of relapsed disease.

The TTP and OS results of this study will be compared with reported outcomes in published trials of Zevalin alone to assess whether there is sufficient improvement to merit further study of this approach in this setting. We have designed the trial to detect an increase in 1-year PFS from a historical value of 50% to 67.3%, which corresponds to an increase in median TTP from 12 months to 21 months.

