- d. Toxicity Assessment: Adverse events are to be recorded on an ongoing basis and on appropriate source documents at the clinical site and in the patient's case report form.

5.E Follow-Up Evaluations

5.E.1 Short-Term Follow-Up Period

- a. The following tests/evaluations will be obtained at 6-month intervals (+/- 7 days) for a period of 2 years (24 months) following the Zevalin:
 - History & Physical examination, including vital signs (BP, temperature & pulse), height, weight, Body Surface Area (BSA), and performance status (Appendix B).
 - Laboratory tests including:
 - o Complete blood count (CBC) with differential and platelet count
 - o Serum chemistries BUN, creatinine
 - o LDH
 - Disease Assessment (Only required at 6-month intervals for a period of 2 years (24 months) following Zevalin):
 - o Total of all measurable indicator lesions.
 - CT or PET scan of the chest, abdomen and pelvis (Restaging of disease by CT scan is recommended every 6 months up to Month 24, then annually until year 5).

5.E.2 Long-Term Follow-Up Period

- a. The following tests/evaluations will be obtained annually (+/- 30 days) for an additional 3 years after the completion of the Short-Term Follow-Up period:
 - History & Physical examination, including vital signs (BP, temperature & pulse), height, weight, Body Surface Area (BSA), and performance status (Appendix B).
 - Laboratory tests including:
 - o Complete blood count (CBC) with differential and platelet count
 - o Serum chemistries BUN, creatinine
 - LDH
 - Disease Assessment:
 - o Total of all measurable indicator lesions.
 - o CT or PET scan of the chest, abdomen and pelvis

Once the patients have completed the Short-Term Follow-Up period they will continue to be followed for 3 years on an annual basis (+/- 30 days) for survival and disease status. Patients should be followed by physical exam and, if clinically indicated by Good Medical Practice, CT or PET scans. Patients will be followed for 3 years or until patient starts alternate treatment or is removed from study to allow determination of study endpoints.

5.F Disease Progression Evaluations/Off-Study

Patients who develop disease progression during the treatment period and who do not begin other anti-cancer therapy will continue to be followed for routine safety and efficacy for a total of 30 days following any discontinuation of treatment for any cause.

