12 STATISTICAL CONSIDERATIONS

12.A Study Design

This is a two- institution phase II trial to determine the efficacy and safety of the ESHAP-Zevalin combination therapy for the management of relapsed (CD 20+) follicular lymphoma. Patients must have received at least one, but no more than 2 prior treatments for follicular lymphoma.

The primary objective of this phase II clinical trial is to evaluate the 1-year progression-free survival (PFS) of patients with relapsed follicular NHL treated with ESHAP chemotherapy for cytoreduction (2 cycles) followed by Y-90 ibritumomab tiuxetan (Zevalin) radioimmunotherapy, compared to what would be expected historically for patients treated with Zevalin without prior cytoreduction. For this patient population, a 1-year PFS of 67.3% will be considered highly encouraging, compared to an historical rate around 50%. These values correspond to approximate median times to progression of 21 months and 12 months, respectively, assuming exponential survival.

12.B. Sample Size

The planned sample size of 52 evaluable patients is based on testing the null hypothesis that the true 1-year PFS is \leq 50%, versus an alternative hypothesis that the true rate is \geq 67.3% with this therapeutic approach. Based on the number of patients seen at the Arizona Cancer Center with relapsed follicular lymphoma requiring treatment, the anticipated accrual rate is 2 patients per month. It is estimated that accrual to the study would be completed within 26 months. All patients who receive at least one dose of chemotherapy will be considered evaluable and included in the analysis. In the unlikely event that an enrolled patient does not receive treatment, an additional patient will be registered.

12.C Method of Analysis

The following are the design characteristics based on a chi-square test for one binomial population at the one-sided 0.10 significance level. If the true PFS is $\leq 50\%$, then there is a maximum probability of 0.10 of concluding that this treatment approach is sufficiently promising that it should be accepted for further study (false positive rate). Alternatively, if the true PFS is $\geq 67.3\%$, then the maximum probability of

rejecting this treatment approach for further study in this setting is 0.10 (false negative rate), equivalent to a power of 90%.

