At the end of the trial, the observed PFS and response rates will be reported, along with appropriate confidence limits. Kaplan-Meier methods will be used to estimate the survival curve of time-to-progression. Promising results at the conclusion of this trial will justify further study in a larger trial.

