2. MEASURES OF DURATION

- Time to Progression: measured from the date of first study treatment to the first date when progressive disease is documented.
 - a. Progressive Disease (PD)-Free Interval (Duration Of Response): measured, in a responder, from the date when a CR, CCR or PR is first noted to the first date at which progressive disease is observed. An ongoing PD-free interval occurs when there is a responder for whom progressive disease has not been noted.

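### Section 12 tests 1-year PFS without defining it; the only PFS definition leaves out non-NHL deaths, and patients taken off study without progression have no scheduled 1-year status or scoring rule

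*Combined protocol and SAP*

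**What the plan says.** Section 12.A makes 1-year PFS the primary objective, with 50% as the historical rate and 67.3% as the target, and ties both to TTP: "These values correspond to approximate median times to progression of 21 months and 12 months, respectively, assuming exponential survival". Section 12.C tests it as one binomial proportion at one-sided 0.10. The denominator is in 12.B: "All patients who receive at least one dose of chemotherapy will be considered evaluable and included in the analysis". Section 12 gives no PFS event, time origin, deciding assessment or rule for unknown status. Its only time-to-event method is for another endpoint: "Kaplan-Meier methods will be used to estimate the survival curve of time-to-progression".

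Appendix D Table 2 lists PFS for all patients as "Disease progression or death from NHL", measured from trial entry. The same table counts deaths from every cause for overall survival and event-free survival, so its PFS entry is narrower. TTP, in Appendix D item 2, has a different origin: it is "measured from the date of first study treatment to the first date when progressive disease is documented".

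On follow-up, Section 5.E.1 counts visits from Zevalin: "The following tests/evaluations will be obtained at 6-month intervals (+/- 7 days) for a period of 2 years (24 months) following the Zevalin". Sections 6.C.5 and 7.B.2 take patients with altered biodistribution off study. Section 11.A adds withdrawal, investigator judgment and need for other therapy. Section 5.F.1 then asks for one set of tests, with imaging, within 4 weeks. Section 3.A keeps patients with more than 25% residual marrow involvement in follow-up for progression and survival, and 3.B states 5 years of follow-up after treatment.

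**The concern.** A binomial test on all treated patients needs a status at 1 year for each of them. Three things stand in the way.

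- **Event.** If Table 2 is followed, a patient who dies of treatment toxicity at month 4 without progression is counted progression-free at 1 year. Section 6.C.6 reports Grade 4 infections and some fatal skin reactions with the Zevalin regimen, and 8.C warns of potentially fatal infusion reactions, so the case is not fanciful.
- **Early leavers.** Patients removed without progression stay in the denominator, yet no status is scheduled for them at 1 year and no rule says how to score them. Patients with more than 25% marrow involvement are to be followed, but the scan dates run from an infusion they do not receive.
- **Deciding scan.** No scheduled disease assessment falls at 1 year from Cycle 1 Day 1 (C1D1). Appendix A marks disease assessment and CT/PET at 6 and 18 months post Zevalin but not at 12 or 24, although 5.E.1 requires 6-month intervals.

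At stake is whether the go/no-go result depends on choices made after the data are seen.

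**Working it through.** **The plan's own figures (Section 12).** p0 = 0.50, p1 = 0.673, one-sided alpha 0.10, power 0.90.

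n = [(1.2816·√(0.5·0.5) + 1.2816·√(0.673·0.327)) / 0.173]² = 51.54, so 52. This reproduces. Under exponential survival the medians are 12.0 months and 12·ln 2 / (−ln 0.673) = 21.0 months, as stated.

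Cut-off: (31−26)/√13 = 1.387 exceeds 1.282 and (30−26)/√13 = 1.109 does not, so the test rejects at 31 or more of 52. Exact binomial: P(X≥31 | 0.5) = 0.106 and P(X≥31 | 0.673) = 0.906.

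The documents give no counts for non-NHL deaths or unknown status. The counts of 1 to 3 below are assumptions.

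**1. Non-NHL deaths scored as successes, against the TTP-based 50% null**

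- If each patient who died would have been progression-free at 1 year anyway, size stays at 0.106.
- If deaths occur at time zero in patients of average risk (upper bound), p = 0.5 + 0.5d/52. Size for d = 1/2/3 is 0.133/0.166/0.203.

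**2. Unknown status, k patients with true PFS pb between 20% and 50%**

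| Scoring | Success probability under the null | Size, k=1 | Size, k=3 |
|---|---|---|---|
| As success | 0.5 + k(1−pb)/52 | 0.133-0.152 | 0.203-0.280 |
| As failure | 0.5 − k·pb/52 | 0.083-0.096 | 0.048-0.078 |

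The only related rate in the documents is the under-0.5% figure in 5.C.2 for one form of altered biodistribution, which is under 0.3 of 52 patients.

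**3. Timing of scans.** ESHAP completion is read as study day 32 (Cycle 2 Day 4) at the earliest and day 56 (end of Cycle 2) at the latest. Section 8.A.1 contemplates a delay of up to 14 days. Add 28-42 days to the Zevalin regimen (7.B) and 6-8 days to its Day 7-9.

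- Earliest ⁹⁰Y dose: 32 + 28 + 6 = day 66, or 2.2 months (30.44 days per month).
- Latest: 56 + 14 + 42 + 8 = day 120, or 3.9 months.
- With the ±7-day visit window, the 6-month scan falls 7.9-10.2 months from C1D1 and the 12-month scan 13.9-16.2 months.
- If the Appendix A calendar is followed instead, the next scan after the 6-month one is at 18 months post Zevalin, or 19.9-22.2 months from C1D1.

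Under a 12-month exponential median, 2^(−t/12) gives 63-56% progression-free at the earlier scan and 45-39% at the 12-month scan, either side of the 50% null. This assumes progression is found only on scheduled scans and that the historical benchmark is not shifted in the same way.

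**4. Power cost of the fix, cut-off unchanged**

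| Scenario | Success probability under the alternative | Power |
|---|---|---|
| 1/2/3 non-NHL deaths, patients otherwise progression-free | 0.673 − d/52 | 0.846/0.766/0.668 |
| 1/2/3 non-NHL deaths, average risk, at time zero | 0.673(1 − d/52) | 0.868/0.820/0.764 |
| 1 unknown as failure, pb 20% to 67.3% | 0.673 − pb/52 | 0.896 to 0.868 |
| 3 unknown as failures, pb 20% to 67.3% | 0.673 − 3pb/52 | 0.872 to 0.764 |
| 1 death (otherwise progression-free) plus 1 unknown, pb 20% to 67.3% | 0.673 − 1/52 − pb/52 | 0.831 to 0.794 |

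Counting all deaths lowers size against the TTP-based null to 0.063/0.035/0.018 in the first row and 0.083/0.063/0.048 in the second.

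**The case against.** The best defence is that Table 2 is a published standard, and that a progression-type endpoint matches a null taken from TTP. That stands in part: it is why the size need not move at all when non-NHL deaths are left out, and why an all-cause test is conservative here. It does not answer the missing scoring rule, and Section 12 does not say that Table 2 governs. Section 1.E adds that "The TTP and OS results of this study will be compared with reported outcomes in published trials of Zevalin alone", so a toxic death would still appear in the survival comparison, though not in the primary test.

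It is also fair that 3.A and 3.B promise continued follow-up, that 5.F.1 requires imaging at removal, and that 13.C requires forms at progression or death. These narrow the gap without scheduling a 1-year status for patients who leave. Progression can also be found on physical examination, and scanning away from a landmark date is ordinary practice.

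A reader might infer more than the documents support:

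- **That no event or origin is stated anywhere.** Table 2 states both. The gap is that Section 12 does not adopt them, and that PFS and TTP start at different points.
- **That 5.E.2 cuts follow-up before 1 year.** Its sentence, "Patients will be followed for 3 years or until patient starts alternate treatment or is removed from study to allow determination of study endpoints", applies once short-term follow-up is complete, which is after 24 months post Zevalin.
- **That patients removed for deterioration leave without progression.** Section 11.A lists deterioration under disease progression.

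**Conclusion.** The concern holds for the endpoint definition and scoring, not for the sample size: 52 reproduces. Section 12 leaves the PFS event, origin, deciding assessment and treatment of unknown status unstated. The one available definition would, if followed, credit a non-NHL death without progression as a success.

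With assumed counts of 1 to 3, size stays at 10.6% or rises to as much as 13/17/20% for deaths scored as successes. For unknown patients it runs from 5-10% to 13-28% according to the scoring rule alone. A reader might quote 17/24/34% for the deaths, from p = 0.5 + d/52. Those rates require true all-cause 1-year PFS to be exactly 50%, whereas the documents tie the 50% to TTP, so they are an illustration only. The scan-timing percentages likewise show how far the choice of scan could matter; they are not an established bias. This should be fixed before the analysis.

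**What to change.** - **Definition.** In Section 12 and Appendix D, define primary PFS from one stated origin (for example C1D1) to documented progression or death from any cause. Report the progression-only 1-year rate beside it, because the null is TTP-based.
- **Follow-up.** Reconcile 3.A and 3.B with the off-study wording in 6.C.5, 7.B.2 and 11.A, so that progression and survival status are collected to 1 year in every ESHAP-treated patient who does not refuse, including those who never receive Zevalin.
- **Assessment.** Reconcile 5.E.1 with Appendix A, and state which disease assessment, with a window, settles 1-year status (for example 12 months ± 30 days from C1D1).
- **Scoring.** Prespecify how unknown status is scored in the binomial test, for example as failure, with a Kaplan-Meier 1-year PFS estimate as sensitivity. State also how new therapy before progression is scored; conventions differ, and the point does not depend on which is chosen.

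The cost is wording, status follow-up for early leavers, and one dated assessment in patients still progression-free at 1 year: about 26 of 52 at 50% (0.5 × 52) or 35 at 67.3% (0.673 × 52). N stays 52. The price is power: about 85/77/67% with 1/2/3 non-NHL deaths in patients otherwise progression-free (87/82/76% if average-risk), 0.90-0.76 with 1 to 3 unknowns scored as failures, and 0.83-0.79 with one of each. Complete 1-year status collection keeps the unknown-status part of that loss small.
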